2.7.3 Atrial Electromechanical Delay

Tissue Doppler Echocardiography will be performed by transducer frequencies of 3-4MHz, adjusting the spectral pulsed Doppler signal filters until a Nyquist limit of 15-20cm/s and using the minimal optimal gain. The monitor sweep speed will be set to 50-100mm/s to optimize the spectral delay of myocardial velocities. In apical 4-chamber view, the pulsed Doppler sample volume will be placed at the lateral and septal sides of the mitral annulus and the right-ventricular (RV) tricuspid annulus to obtain tissue Doppler velocities. The time intervals from the onset of the P wave (ECG) to the beginning of the Am wave (on echo) will be measured from the lateral mitral annulus (lateral PA), septal mitral annulus (septal PA), and RV tricuspid annulus (tricuspid PA). The timing of mechanical activation of each sample point is dependent on the distances of each point to the sinoatrial node (SA). Accordingly, the RV tricuspid annulus is the earliest (closest) and the lateral mitral annulus is the latest (farthest) point to be activated by impulses from the SA node. The difference between any two reference points reflects the mechanical delay between these two points Inter-AEMD will be defined as the difference between the lateral PA and tricuspid PA, intra-right AEMD will be defined as the difference between the septal PA and tricuspid PA, and intra-left AEMD will be defined as the difference between the lateral PA and septal PA.

2.6.3 Signal Averaged ECG

Signal averaged-ECG will be recorded at St. Michael's hospital. Acquisition and analysis will be performed in the same manner in which the athletes without AF would have received at a prior visit for another REB-approved study. Briefly, the subject will be in supine position, in a room free from electrical interference. Three bipolar orthogonal leads (x,y,z) will be used. Electrode placement will be according to the following: X

electrodes in the left and right mid-axillary line of the 4th intercostal space; Y electrodes in the left mid-clavicular line at the level of the abdomen; Z electrode placed in the mid-clavicular line in the 4th intercostal space. A P-wave template will be generated and averaged P-wave signals will be filtered using a spectral filter. Measurements will include filtered P-wave duration (ms) and root mean square voltage in the terminal 20 ms of the P-wave (mv).

2.7.4 Cardiac Magnetic Resonance Imaging

All athletes with AF will undergo resting cardiac magnetic resonance imaging (cMRI) at St. Michael's hospital, following methods used for previous REB-approved study). MRI will be performed supine in a 3.0T scanner (Siemens MAGNETOM Skyra 3.0T with TIM and DOT technology); images will be obtained on end-expiration breath holds. Vertical long-axis cine images will be prescribed from axial scout images by aligning the left ventricular (LV) apex with the center of the mitral valve. From these LV long-axis images, the horizontal long-axis plane will be obtained by aligning the midpoint of the left ventricular apex and mitral valve. These pilot 4-chamber and 2-chamber views provide the reference images on which a stack of contiguous short-axis slices will be prescribed, covering the left atrium and left ventricle. Depending on the LV long-axis length, 8-12 contiguous slices will cover the entire left ventricle. Providing normal creatine levels are verified (see above), delayed enhancement MRI will be acquired 10 minutes after contrast agent injection of gadolinium (0.1 mmol/kg body weight, Multihance, Bracco Diagnostic Inc, Princeton, NJ) (MRI contrast agent does not contain iodine and does not damage the kidneys. Subjects refusing gadolinium will still be studied. Imaging will be used for cardiac structure and volumetric assessments of the

atria and ventricles (max and min volume, EDV and ESV). All data analysis will be performed using CMR42 (Circle Imaging, Calgary, Canada). End-diastolic frames are defined as the image with the largest ventricular volume in each series, and end-systolic as the image with the smallest volume. Endocardial and epicardial borders on these frames will be manually traced. From this data, LV and RV ejection fraction, end diastolic/end systolic and stroke volume indices will be calculated. Manual tracing of endocardial borders of short-axis images at atrial end-diastole and atrial end-systole will allow for calculation of LA end-diastolic volume and end-systolic volume.

2.8 Data Analysis

All variables will be expressed as mean and standard deviation. Differences in outcome measures (AEMD, atrial phasic function, atrial dimensions) will be assessed using a series of independent t-tests between the athletes with AF and athletes without AF. A 2-way repeated measures analysis of variance (ANOVA) will be used to compare resting and exercise values between and within groups. Covariates will be included when appropriate, including age, years since AF diagnosis, and number of AF episodes. Atrial size and relation to ECG parameters may be studied for correlational analyses.

Significance will be set at $p < 0.05$. Analysis will be performed using SPSS software.

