2.2 Sample Size

The primary outcome measure for the first hypothesis is atrial reservoir function, as measured by myocardial strain imaging by echocardiography. There are no data describing atrial phasic function in athletes with AF. Accordingly sample size was determined using the average difference in reservoir strain in a cohort of middle aged (51.78 ± 6.83 years) patients with lone AF, compared to healthy middle aged (48.97 ± 7.65 years) controls with no presence of AF or other cardiovascular related disease. Left atrial reservoir strain was reported as: (29.01 ± 5.63 %) in patients with AF compared to (35.5 ± 4.77 %) in healthy adults. Accordingly, the mean difference between groups was 6.49 ± 5.2 . Thus, based on an alpha of 0.05 and power of 0.8, 11 participants are necessary in each group.

The primary outcome measure for the second hypothesis is AEMD. No previous literature has examined AEMD in endurance athletes, nor is there established reference values for healthy adults. Previous literature has demonstrated patients with paroxysmal AF to have significantly greater delays in inter-atrial EMD, as well as both left and right AEMD. However, it has been suggested that specifically intra-left AEMD is a significant marker for the development of AF, and was correlated to P-wave dispersion, left atrial diameter and left atrial area ⁽⁴⁵⁾. Accordingly, sample size was determined using the difference in left AEMD in a cohort of otherwise healthy middle-aged patients (48.3 ± 11.1 years) with lone AF compared to healthy middle-aged (45.2 ± 4.8 years) controls with no presence of lone AF. Left-atrial EMD was reported as: 21.8 ± 9.1 ms in AF patients and 14.1 ± 4.9 ms in controls (difference of 7.7 ± 7 ms). Thus, based on an alpha of 0.05 and power of 0.8, 15 participants are necessary in each group (n=30).

Accordingly, the more conservative calculation of 15 per group will be used. However, in our experience, poor imaging quality lead to unanalyzable data may occur in 10-15% of the sample, therefore we will recruit 17 per group to ensure adequate statistical power.

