2.4 Methods

General Procedures

All participants will be assessed at the same time of day. Participants will be asked to abstain from exercise on the day before and the day of each study visit.

Visit One: Participant Screening/Consent/ Graded Exercise Testing /

Echocardiography

The first visit will take place at the Heart Health Laboratory. Prior to attending the first visit, participants will have received consent forms and a 2-week Exercise Diary through email. Participants will complete consent form and have the opportunity to ask questions as needed upon their first visit, as well as return the 2-week Exercise Diary. Participants will be then familiarized with the procedures of the study. Participants will undergo basic anthropometric assessment to determine body mass (weight and height) and resting blood pressure. Following this, participants will be fitted with a 12-lead ECG and proceed to complete resting and submaximal exercise echocardiography, performed by a trained sonographer. Emphasis will be on left atrial volume, phasic function and AEMD. Exercise will be on a semi-recumbent cycle ergometer designed for stress echocardiography (Ergoline 1200EL). Imaging will be performed at rest, followed by a two-minute warm up. Participants will then cycle at 100 bpm for 5 minutes and at 130 bpm for 5 minutes; imaging will be initiated 2 minutes into each stage. During a 30-min rest period, participants will complete a Lifetime Physical Activity Questionnaire

Participants will then proceed to have a maximal cardiopulmonary exercise treadmill test with a HR monitor (Polar V800).

Visit Two: Resting Signal Averaged ECG/ Cardiac Magnetic Resonance Imaging/Holter Monitor

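### The repeated-measures ANOVA for the exercise hypothesis conventionally drops anyone with one unreadable stage; a mixed model would use all available stages

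*Combined protocol and SAP*

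**What the plan says.** Section 1.3 (Hypotheses) expects left atrial strain to be impaired in athletes with AF at rest and in submaximal exercise, with the larger deficit in exercise. The second part is a question about a group-by-stage interaction.

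Section 2.4 (Methods, Visit One) images first at rest. Then: "Participants will then cycle at 100 bpm for 5 minutes and at 130 bpm for 5 minutes", with imaging started two minutes into each stage. Each participant therefore has up to three acquisitions.

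Section 2.8 (Data Analysis) plans independent t-tests between groups for AEMD, atrial phasic function and atrial dimensions. For the exercise data it says: "A 2-way repeated measures analysis of variance (ANOVA) will be used to compare resting and exercise values between and within groups". The software is SPSS. The section does not give the number of within-person levels, the SPSS procedure or the handling of a participant with a missing stage.

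Section 2.2 (Sample Size) sizes both hypotheses as two-group comparisons of means. For strain, "the mean difference between groups was 6.49 ± 5.2" and "based on an alpha of 0.05 and power of 0.8, 11 participants are necessary in each group". AEMD needs 15, and "the more conservative calculation of 15 per group will be used". It then warns that "unanalyzable data may occur in 10-15% of the sample" and recruits 17 per group. No calculation covers the repeated-measures ANOVA or its interaction.

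**The concern.** A conventional repeated-measures ANOVA needs a value at every within-person level. A participant whose 130 bpm images cannot be read leaves that analysis altogether, and the readable rest and 100 bpm values leave it too. Images taken during cycling are an obvious place for stage-specific loss, and the investigators already expect some unreadable images.

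What is at stake is the precision of the only planned test of whether the deficit is larger in exercise. No sample size calculation protects that test, so readable data should not be discarded from it without need. There is also a question of selection. Complete-case analysis needs stronger assumptions about why stages are missing than a likelihood-based model fitted to every available stage.

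**Working it through.** **Inputs.** From section 2.2: strain difference 6.49, SD 5.2; AEMD difference 7.7 ms, SD 7 (pooling 9.1 and 4.9 gives √((9.1² + 4.9²)/2) = 7.31); alpha 0.05 (taken as two-sided), power 0.80; 17 recruited per group; loss 10-15%. From section 2.4: three imaging stages. Assumed, because the documents give no figure: within-person correlation ρ = 0.6, equal at all pairs of stages, and the pattern of loss across stages.

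**Step 1: the plan's own figures.** Two-group comparison, 1:1.
- Strain: 11 by the normal formula, 11.1 by the noncentral t. Stated: 11.
- AEMD: 13 (normal) or 14.0 (t) with SD 7; 15 or 15.2 with SD 7.31. Stated: 15.
- Inflation: 15/0.90 = 16.7, so 17; 15/0.85 = 17.6, so 18. Stated: 17.

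These agree closely enough to proceed.

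**Step 2: complete cases per group from 17, with loss d.**

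| Reading of the 10-15% | Formula | d = 10% | d = 15% |
|---|---|---|---|
| Per participant, as worded (or per stage, same people every time) | 17(1 − d) | 15.3 | 14.5 |
| Per stage, latent correlation of loss 0.9 | Gaussian copula | 14.5 | 13.3 |
| Per stage, latent correlation of loss 0.5 | Gaussian copula | 13.3 | 11.8 |
| Per stage, independent, three levels | 17(1 − d)³ | 12.4 | 10.4 |
| Per stage, independent, two levels only | 17(1 − d)² | 13.8 | 12.3 |

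The range is about 10 to 15. The lower end needs both a per-stage rate and independence within a person.

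**Step 3: cost to the interaction contrast.** The contrast is the group difference in (130 bpm minus rest).
- Complete-case variance: 2 × 2σ²(1 − ρ) / [17(1 − d)³]. With σ = 5.2 and ρ = 0.6 the numerator is 4 × 27.04 × 0.4 = 43.26, giving 43.26/12.39 = 3.49 at 10% and 43.26/10.44 = 4.14 at 15%.
- All-available variance: per group, add the inverse covariance of the observed stages over all patterns of missingness, each weighted by its probability and by 17. Invert, take the contrast, and double it for two groups.
- Ratio of complete-case to all-available variance, independent loss: 1.19 at 10% and 1.30 at 15% using expected information; simulated missingness patterns gave 1.19 and 1.35. In standard error that is √1.19 = 1.09 to √1.35 = 1.16.
- Latent correlation of loss 0.5: 1.11-1.17. Latent correlation 0.9: 1.04-1.06. Same people lost at every stage: 1.00.

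If the 10-15% counts participants with any unreadable stage, the ratio cannot exceed that against full data: 1/0.90 = 1.11 to 1/0.85 = 1.18.

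**Step 4: power where it can be computed.** For a two-group t-test on the planned strain difference, power is 75% at 10 per group, 80% at 11, 83% at 12 and 91% at 15. Power for the interaction cannot be computed, because the plan gives neither an interaction effect nor a within-person correlation.

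**The case against.** The strongest reply is that the plan, as worded, has already allowed for image loss. The 10-15% is a share of participants, and 17 per group was chosen to keep 15. A reader might infer that the plan's own loss rate shrinks the exercise analysis to 10-12 per group. The documents do not support that: the figure appears only when the rate is moved to each stage and losses are made independent. Poor imaging windows may well recur in the same person, which pulls the count back up. This objection stands and limits the size of the point.

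A reader might also infer that resting data are lost to the study. They are not. The t-tests in section 2.8 are separate, and a participant with readable rest images stays in them.

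Third, a reader might infer that the complete cases are biased because athletes with AF, who may be on rate control (section 2.0), will fail more often at 130 bpm. That is a plausible risk, but no passage gives a rate or says that anyone will miss the stage. Missingness related only to group does not bias a model that contains group. Bias needs missingness related to the outcome within group.

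Finally, section 2.8 states neither three levels nor complete-case use. Both are inferred, from section 2.4 and from how the named method conventionally works. That inference is reasonable, and nothing in the plan points to another handling.

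These replies do not remove the core: the named method discards readable stages whenever loss is stage-specific, and a better method is available in the same software.

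**Conclusion.** The concern holds in a limited form. The method named for the exercise part of hypothesis 1 conventionally excludes anyone with one unreadable stage, and the plan has no rule to prevent this. On the plan's wording about 14.5-15.3 per group remain, and the cost is small. If the same rate applies per stage, complete cases lie between about 10 and 15 per group. At the worst of the patterns examined (independent loss, ρ assumed 0.6), the variance of the interaction contrast is about 1.2-1.35 times larger, or 9-16% in standard error. If the same people are lost throughout, there is no penalty.

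Even 10-12 per group would leave 75-83% power for a simple strain difference of the planned size, so this is a matter of avoidable imprecision and does not sink the study. Higher loss in exercise could make it worse, but the documents give no such rate. The change is worth making because it costs almost nothing and the interaction has no sample size of its own.

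**What to change.** In section 2.8, replace the repeated-measures ANOVA with a linear mixed model (SPSS MIXED, REML):
- fixed effects for group, stage (rest, 100 bpm, 130 bpm) and group by stage;
- unstructured covariance across the three stages, which also removes the sphericity assumption;
- Satterthwaite or Kenward-Roger degrees of freedom;
- every available stage used, with the group-by-stage term as the test of a larger deficit in exercise.

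In section 2.2, say whether the 10-15% is per participant or per stage, and whether it covers the exercise images.

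Report the number of missing stages by group, with the reason (unreadable image, stage not reached, not in sinus rhythm). This is needed because the mixed model does not remove bias if missingness depends on the unseen value.

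The cost is a few sentences in the plan, with the same participants, data and software. The small downside is slightly more modelling in a small sample. With complete data the conclusions should be essentially the same as from the ANOVA.
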